3 STUDY OBJECTIVES

The objective of this study is to evaluate the efficacy and safety of RBC transfusion for support of acute anemia in cardiovascular surgery patients based on the clinical outcome of renal impairment following transfusion of RBCs treated with the INTERCEPT Blood System for Red Blood Cells compared to patients transfused with conventional RBCs.

Cerus Corporation

Title: A Randomized, Double-Blinded, Controlled, Parallel Group, Non-inferiority, Phase III Study to Evaluate the Efficacy and Safety of the INTERCEPT Blood System for Red Blood Cells in Patients undergoing Complex Cardiac Surgery Procedures (the ReCePI study)

4 INVESTIGATIONAL PLAN

4.1 ENDPOINTS

4.1.1 Primary Endpoints

The primary efficacy endpoint is the proportion of patients, who have received at least one study transfusion with a diagnosis of renal impairment defined as:

- Any raised sCr level, occurring after transfusion of a study RBC, of ≥ 0.3 mg/dL (or 26.5 μ mol/L) from the pre-surgery baseline within 48 ± 4 hours of the end of surgery.

If any subject meets this criterion before receiving a study transfusion, that particular event will not be included in the primary endpoint analysis. The treatment comparison for the primary efficacy endpoint will be assessed by a non-inferiority test (Test–Control) with a non-inferiority margin of 50% increase from the Control rate and two-sided 0.05 alpha level. Patients who receive a study transfusion but die within 48 hours after surgery will be included in the mITT analysis but excluded from the per protocol analysis.

The primary safety endpoints are:

- Proportion of patients with any treatment-emergent adverse events (TEAEs) possibly, probably or definitely related to study RBC transfusion through 28 days after the last study transfusion; and
- Proportion of patients with treatment-emergent antibodies with confirmed specificity to INTERCEPT RBCs by end of study (i.e., 75 ± 15 days after the last study transfusion).

TEAEs by definition will comprise all untoward medical events occurring after the start of the first study RBC transfusion and during the study (i.e., adverse events, serious adverse events, unanticipated adverse device effects, TRs and within 28 days post last study RBC transfusion). The primary safety endpoint is focused on possibly, probably or definitely related adverse events to the study RBC transfusion, because these patients have many adverse events which are unrelated to study RBC transfusion.

Cerus Corporation

Title: A Randomized, Double-Blinded, Controlled, Parallel Group, Non-inferiority, Phase III Study to Evaluate the Efficacy and Safety of the INTERCEPT Blood System for Red Blood Cells in Patients undergoing Complex Cardiac Surgery Procedures (the ReCePI study)

4.1.2 Secondary Endpoints

- Efficacy: Secondary efficacy endpoints include:
 - The proportion of patients with a diagnosis of stage I, II or III Acute Kidney Injury (KDIGO 2012) based on changes in sCr levels from pre-surgery baseline and the need for renal replacement therapy (RRT) post-surgery.
 - Mortality or the need for RRT by 30 days post completion of surgery.

Safety: Assessment of additional safety parameters in post-surgical subjects transfused with INTERCEPT RBCs compared with subjects transfused with conventional RBCs, include:

- Treatment-emergent AEs through 28 days after the last study transfusion.
- Treatment-emergent SAEs through 28 days after the last study transfusion.
- Transfusion reactions (as defined by the CDC National Healthcare Safety Network [NHSN] Hemovigilance Module protocol) through 28 days after last study transfusion.
- Treatment-emergent immunization to RBC allo-antigens through 28 ± 3 days after the last study transfusion.
- Treatment-emergent immunization to HLA allo-antigens through 28 ± 3 days after the last study transfusion.

[figure not shown]
Cerus Corporation

Title: A Randomized, Double-Blinded, Controlled, Parallel Group, Non-inferiority, Phase III Study to Evaluate the Efficacy and Safety of the INTERCEPT Blood System for Red Blood Cells in Patients undergoing Complex Cardiac Surgery Procedures (the ReCePI study)

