Newly-emerging infectious agents also remain important risks to blood safety. Estimates of per-unit and per-patient aggregate infectious risks for conventional RBCs, including known and potential emerging infectious agents (EIA, modeled based on chikungunya and dengue viruses) were calculated by Kleinman and Stassinopoulos (2015). Minimum and maximum per-unit risks were calculated as 0.0003% (1/323,000) and 0.12% (1/831), respectively. The minimum estimate is for known lower-risk pathogens while the maximal estimate also includes an EIA and endemic area *Babesia* sp. risk. For patients with hemoglobinopathies who receive repeated RBC transfusions such as sickle cell disease (SCD), at the minimum risk level it is estimated that approximately 1/450 (0.22%) of patients will acquire an infection during their entire course of transfusion therapy (approximately 30-50 years); at the maximum risk levels, infections risk increases to 43-45% for patients with hemoglobinopathies, or almost 1 in every 2 patients (Kleinman and Stassinopoulos 2015).

Leukoreduced RBC concentrates contain $<5 \times 10^6$ white blood cells (WBC) that may induce TA-GVHD and/or alloimmunization to human leukocyte antigen (HLA) antigens. Gamma irradiation can effectively prevent TA-GVHD in transfusion recipients. However, almost half the cases of TA-GVHD occur in patients in which their treating physicians failed to identify risk using current guidelines for blood irradiation, leading to substantial morbidity and mortality (Kopolovic 2015). Moreover, irradiation adversely affects post-transfusion RBC recovery (Dumont 2008) and is associated with raised extracellular potassium levels in the transfused concentrates.

To proactively address the risk of TTIs and TA-GVHD, Cerus has developed pathogen and leukocyte inactivation technology systems (INTERCEPT Blood System™) for platelet and plasma components and is currently developing a system for RBC concentrates. These systems use nucleic acid-targeted compounds that intercalate into, and upon activation, covalently bind to nucleic acids of viruses, bacteria, parasites and leukocytes that may contaminate blood components, and form irreversible adducts and crosslinks thus preventing replication and TTI. This

Cerus Corporation

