Title: A Randomized, Double-Blinded, Controlled, Parallel Group, Non-inferiority, Phase III Study to Evaluate the Efficacy and Safety of the INTERCEPT Blood System for Red Blood Cells in Patients undergoing Complex Cardiac Surgery Procedures (the ReCePI study)

process does not depend on or generate reactive oxygen species (ROS) which can damage cells and proteins. RBCs do not require nucleic acid for therapeutic function and thus retain therapeutic efficacy after pathogen inactivation treatment.

INTERCEPT treated RBC (INTERCEPT RBCs) components should not require gamma irradiation because the treatment process inactivates donor white blood cells with a high safety margin (Castro et al. 2016). It is also possible that INTERCEPT treatment may interfere with antigen presentation by donor leukocytes, thereby reducing the incidence of HLA alloimmunization.

Conventional leukoreduced RBC concentrates include approximately 20-40 mL of residual plasma that contains serum proteins and immunoglobulins; these are implicated in allergic TRs and Transfusion Related Acute Lung Injury (TRALI). The INTERCEPT RBC process includes a terminal washing step that reduces the concentration of plasma proteins and may reduce the incidence of these reactions.

The INTERCEPT Blood System for RBCs inactivates a variety of bacteria, viruses and protozoa. The organisms evaluated to date include examples representing a range of different characteristics, such as enveloped (HIV and DHBV) and non-enveloped (Bluetongue virus), RNA genome (HIV and BVDV) and DNA genome (DHBV), and single stranded (HIV) and double stranded (DHBV) genomes. The bacteria evaluated represent Gram negative bacilli (*Yersinia* sp., *Serratia* sp., *E. coli*, *Salmonella* sp. and *Pseudomonas* sp.) and Gram positive cocci (*S. epidermidis* and *S. aureus*) that are significant especially for RBC transfusion. The protozoan parasites evaluated to date are *Plasmodium falciparum* and *Babesia microti*. INTERCEPT RBCs have demonstrated adequate viability in terms of in vivo recovery and lifespan for transfusion (Cancelas 2015), and a recently completed Phase 3 clinical study (CLI 00076) in cardiovascular surgery patients conducted in Europe has demonstrated that INTERCEPT RBCs possess in vitro characteristics comparable to untreated RBCs with a comparable safety profile (Brixner 2015, Rico 2015).

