2.4 SUMMARY OF POTENTIAL RISKS

The potential risks of this study include those adverse reactions that are recognized to occur following any transfusion of RBC components and could be anticipated to occur with either control or INTERCEPT-treated components including, but not limited to, delayed serologic transfusion reactions (DSTRs), acute hemolytic transfusion reactions (AHTRs), delayed hemolytic transfusion reactions (DHTRs), febrile non-hemolytic transfusion reactions (FNHTRs), allergic (urticarial) reactions, anaphylaxis, transfusion-related acute lung injury (TRALI), transfusion-associated circulatory overload (TACO), transfusion-related sepsis (TRS), or transfer of an infectious agent via transfusion/transfusion transmitted infection (TTI), respectively, transfusion- associated graft-vs-host disease (TA-GVHD), and allo-immunization to RBC and HLA antigens.

The development of antibodies to INTERCEPT RBCs, or to neoantigens formed as a result of acridine binding to red cells, could occur as a result of transfusion with INTERCEPT RBCs. Acridine-specific antibodies were observed in an early and current ongoing blinded studies (as described in the Investigator's Brochure) and many could be neutralized with acridine in solution, thereby defining specificity for this moiety. The occurrence of these antibodies was not associated with any clinical events or observations. The Current process has been optimized to decrease the likelihood of this event.

A screening study was performed to evaluate the prevalence of natural antibodies with specificity for INTERCEPT RBCs (SUD 00742). Five plasma samples from 998 subjects requiring chronic transfusion support for anemia and 12 plasma samples from 10,721 hospital subjects demonstrated low titer cross-reactions with INTERCEPT RBCs. The cumulative prevalence of cross-reactive antibodies to INTERCEPT RBCs was 0.15%. Each of the antibodies identified was characterized and none were found to be IgG₁ or IgG₃ subclass, the antibody subclasses most associated with physiologic hemolytic activity. The majority demonstrated specificity for acridine.

Several instances of treatment emergent antibodies with specificity for INTERCEPT RBCs were reported during the ongoing Phase III clinical investigations. In each event, the antibodies were shown to be non-clinically significant without evidence of patient harm. These studies remain blinded and it is not known whether the patients received Test of Control RBCs.

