7.3.1.10 Definition of Transfusion Reaction

A transfusion reaction is defined as an undesirable response or effect in a patient temporally associated with and possibly, probably or definitely related to the administration of blood or blood components. The current version of the CDC NHSN Hemovigilance Protocol definitions must be used when recording transfusion reaction

Cerus Corporation

Title: A Randomized, Double-Blinded, Controlled, Parallel Group, Non-inferiority, Phase III Study to Evaluate the Efficacy and Safety of the INTERCEPT Blood System for Red Blood Cells in Patients undergoing Complex Cardiac Surgery Procedures (the ReCePI study)

terms in this study ([APPENDIX 3](#)).

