7.4 REPORTING PERIOD

All safety events will be collected from the start of surgery or the start of the first study transfusion (whichever is first) through 28 days after the last study transfusion or death, whichever is first.

Vital status and need for RRT of all subjects will be collected at 30 days after the end of surgery and at the end of study visit (Day 75 ±15 days).

Blood sample for assessment of sCr will be collected on post-operative day 2 (at 48 ± 4 hours post end of surgery) for the primary endpoint. For non-transfused subjects, a blood sample for sCr will be drawn at 48 ± 4 hours post-surgery.

Blood samples for assessment of INTERCEPT RBC-specific antibody, HLA antibodies and chemistry and hematology laboratory studies at 28±3 days after the last study transfusion.

Blood samples for assessment of INTERCEPT RBC-specific antibody will also be obtained 75 ±15 days after the last study transfusion.

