
Definitive: Positive direct antiglobulin test (DAT) for antibodies developed between 24 hours and 28 days after cessation of transfusion
 
AND EITHER
 
Positive elution test with alloantibody present on the transfused red blood cells
 
OR
 
Newly-identified red blood cell alloantibody in recipient serum
 
AND EITHER
 
Inadequate rise of post-transfusion hemoglobin level or rapid fall in hemoglobin back to pre-transfusion levels
 
OR
 
Otherwise unexplained appearance of spherocytes.
	
Non-severe: Medical intervention (e.g. symptomatic treatment) is required but lack of such would not result in permanent damage or impairment of a bodily function.
 
Severe: Inpatient hospitalization or prolongation of hospitalization is directly attributable to the adverse reaction, persistent or significant disability or incapacity of the patient occurs as a result of the reaction, or a medical or surgical intervention is necessary to preclude permanent damage or impairment of a body function.
 
Probable: Newly-identified red blood cell alloantibody demonstrated between 24 hours and 28 days after cessation of transfusion
 
BUT Incomplete laboratory evidence to meet definitive case definition criteria.
 
NOTE: Patient may be asymptomatic or have symptoms that are similar to but milder than AHTR; symptoms are not required to meet case definition criteria.
	
Definite: No other explanation for symptoms or newly-identified antibody is present.
 
Probable: An alternate explanation for symptoms or newly-identified antibody is present, but transfusion is the most likely cause.
 
Possible: Other explanations for symptoms or newly-identified antibody are more likely, but transfusion cannot be ruled out.

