Definitive: A clinical syndrome occurring from 2 days to 6 weeks after cessation of transfusion characterized by: 
 Characteristic rash: erythematous, maculopapular eruption centrally that spreads to extremities and may, in severe cases, progress to generalized erythroderma and hemorrhagic bullous formation. Diarrhea Fever Hepatomegaly Liver dysfunction (i.e., elevated ALT, AST, Alkaline phosphatase, and bilirubin) Marrow aplasia Pancytopenia AND Characteristic histological appearance of skin or liver biopsy.	Non-severe: N/A Severe: Patient had marked symptoms and responded to treatment. Life-threatening: Patient had severe symptoms and required life-saving treatment (e.g., immunosuppression). Death: The recipient died as a result of the adverse transfusion reaction . Death should be used if death is possibly, probably or definitely related to transfusion. If the patient died of a cause other than the transfusion, the severity of the reaction should be graded as appropriate given the clinical circumstances related to the reaction.	Definite: WBC chimerism present in the absence of alternative diagnoses. Probable: WBC chimerism present BUT Other potential causes are present (e.g., stem cell transplantation). Possible: WBC chimerism not present or not done OR Alternative explanations are more likely (e.g., solid organ transplantation).
Probable: Meets definitive criteria EXCEPT Biopsy negative or not done.		OPTIONAL
Possible: N/A	Not Determined: The severity of the adverse reaction is unknown or not stated.	Doubtful: Evidence is clearly in favor of a cause other than the transfusion, but transfusion cannot be excluded. Ruled Out: There is conclusive evidence beyond reasonable doubt of a cause other than the transfusion. Not Determined: The relationship between the adverse reaction and the transfusion is unknown or not stated.

Cerus Corporation

Title: A Randomized, Double-Blinded, Controlled, Parallel Group, Non-inferiority, Phase III Study to Evaluate the Efficacy and Safety of the INTERCEPT Blood System for Red Blood Cells in Patients undergoing Complex Cardiac Surgery Procedures (the ReCePI study)

NHSN Biovigilance Component
Hemovigilance Module Surveillance Protocol v2.5.2
www.cdc.gov/nhsn

Post transfusion purpura (PTP)

Case Definition	Severity	Imputability

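### Transfusion reactions are collected only through Day 28, but the adopted NHSN definition of TA-GVHD allows onset up to 6 weeks, so onset on Days 29-42 is not prompted for (minor)

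*Protocol*

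**What the plan says.** Section 4.1.2 of the protocol counts "Transfusion reactions (as defined by the CDC National Healthcare Safety Network [NHSN] Hemovigilance Module protocol) through 28 days after last study transfusion", and Section 7.3.1 repeats this. Section 7.3.1.10 ties classification to NHSN: "The current version of the CDC NHSN Hemovigilance Protocol definitions must be used when recording transfusion reaction" terms. Section 7.4 ends collection of all safety events "through 28 days after the last study transfusion or death, whichever is first". Sections 6.1.4 and 7.5.5 agree, and Table 7.1e marks AEs, SAEs and transfusion reactions only in the 28±3 day column.

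Appendix 3 (NHSN v2.5.2) lists TA-GVHD among its defined reactions. Its definitive case definition begins "A clinical syndrome occurring from 2 days to 6 weeks after cessation of transfusion characterized by". By contrast, the delayed hemolytic reaction is defined by a "Positive direct antiglobulin test (DAT) for antibodies developed between 24 hours and 28 days after cessation of transfusion", and the delayed serologic reaction also ends at 28 days.

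Two contacts come after the 28-day rule, or close to it. The Day 30 assessment (Section 6.1.5) asks for vital status and renal replacement therapy (RRT). The visit at 75±15 days after the last study transfusion (Section 6.1.6) asks for vital status, RRT and the INTERCEPT-specific antibody. Section 6.1.6 also sends a positive S-303-specific serologic reaction found at that visit to the AE eCRF.

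**The concern.** One follow-up length is applied to reaction types whose definitions run over different periods. Twenty-eight days suits the delayed hemolytic and serologic reactions but stops two weeks short of the TA-GVHD definition.

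TA-GVHD is not incidental to this product. Section 2.1 says the systems were developed "To proactively address the risk of TTIs and TA-GVHD" and that treated red cell "components should not require gamma irradiation because the treatment process inactivates donor white blood cells with a high safety margin". The same section describes TA-GVHD as a fatal complication, and Section 2.4 lists it among the potential risks of the study. If no TA-GVHD is reported under the endpoint, that result covers onset only through Day 28, although the definition runs to Day 42. A later analysis plan cannot repair this, because it cannot recover events that were not sought.

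**Working it through.** The 28-day window is a chosen length, so there is no computed figure in the plan to reproduce. The check compares windows and contact dates.

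**Inputs**
- Collection end: 28 days after the last study transfusion (Sections 4.1.2, 7.4, 7.5.5).
- TA-GVHD onset: 2 days to 6 weeks after transfusion (Appendix 3), and 6 × 7 = 42 days.
- Study transfusions: Day 0 to Day 7 (Section 4.4).
- Planned size: 146 per arm (Section 8.2).

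**Uncovered days**
- Causal unit is the last study unit: 42 - 28 = 14 days (Days 29-42).
- Causal unit on Day 0, last unit on Day 7: collection reaches 7 + 28 = Day 35 after the causal unit, leaving 42 - 35 = 7 days.

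**Does any planned contact close the gap?** In days after the last study transfusion:

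| Contact | Days | Asks about TA-GVHD with onset on Days 29-42? |
|---|---|---|
| Day 30 post-surgery | 30 - 7 = 23 to 30 - 0 = 30 | No; vital status and RRT |
| 28±3 visit | 25 to 31 | Reaction collection stops at Day 28 |
| 75±15 visit | 60 to 90 | No; vital status, RRT, antibody |

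No contact falls on Days 32-42. The 75±15 visit comes 60 - 42 = 18 to 90 - 42 = 48 days after the TA-GVHD window closes, so one retrospective item there would cover the whole window.

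**Does the statistics section change?** With zero events in 146 Test patients, the one-sided 95% upper bound is 1 - 0.05^(1/146) = 2.03% under either window. The primary endpoint is read within 48±4 hours of the end of surgery, so the efficacy test and its power do not depend on this.

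**The case against.** The best defence is that nothing is inconsistent. Section 7.3.1.10 adopts NHSN definitions for recording reaction terms. It does not adopt NHSN onset windows as trial follow-up, and the 28-day limit is applied uniformly. That stands. A reader might infer that the protocol contradicts itself; it does not.

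A reader might also infer that a late case would be lost altogether. The documents do not support that. The TEAE definition in Section 8.1.2 has no upper time limit, so a late case that was reported could still be tabulated there. Section 11.3 (unanticipated problems) and Section 7.3.1.4 (unanticipated device effects) state no day limit. A fatal case would appear as a death at Day 75±15, and the autopsy sentence in Section 7.5.5 may bring the cause to light. The eCRF is not shown. What remains is narrower: these routes depend on someone recognising and volunteering the event, and none places it in the 28-day transfusion-reaction endpoint.

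A third tempting inference is that about a third of cases are missed, since 14 of the 41 days from Day 2 to Day 42 are uncovered. That is a share of calendar days. The documents give no onset distribution or incidence, so it measures no loss of cases.

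Expected cases are indeed near zero: both arms are leukoreduced, and patients who require irradiated cells are excluded (Section 5.2). Section 2.1 itself notes, however, that nearly half of cases arise where the treating physician had not identified the risk, so the exclusion does not remove them all.

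Finally, NHSN also has a 6-month item for transfusion-transmitted infection, which could suggest that singling out TA-GVHD is arbitrary. That item is an investigation trigger that depends on later findings in the donor; it is not a case-definition onset window. TA-GVHD is the one reaction in Appendix 3 whose case definition states an onset window longer than 28 days.

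**Conclusion.** The point holds as a minor, inexpensive improvement to safety capture. TA-GVHD with onset on Days 29-42 after the last study transfusion meets the definition the protocol adopts, is not prompted for, and falls outside the 28-day transfusion-reaction endpoint. The gap is 14 days from the last study unit and 7 to 14 days from a unit given on Day 0. Efficacy, power and the zero-event bound are untouched. The case for acting is that a single late case would matter for a product meant to make irradiation unnecessary.

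This rests on the v2.5.2 text in Appendix 3, although Section 7.3.1.10 calls for the current NHSN version; a different onset window there would change the day counts. It also assumes that no unseen eCRF page already asks the question. It should not be read as a finding that causes of late deaths go uncollected, which the documents do not settle.

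**What to change.** Keep 28 days for all other AEs, SAEs and transfusion reactions. In Sections 4.1.2, 7.3.1, 7.4 and 7.5.5 and Table 7.1e, extend the window for TA-GVHD alone to 42 days after the last study transfusion. At the existing Day 75±15 visit, record on the AE eCRF any TA-GVHD with onset by Day 42, using the route already in place for a positive S-303 serologic reaction. Take the information from medical records, including biopsy and chimerism results where available, because NHSN classification relies on them and patient recall cannot supply them. For any such case, also record non-study transfusions since Day 28, since Table 7.1e schedules other blood components only at the 28±3 visit.

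The cost is a small amendment with IRB approval and one eCRF item, with no new visit or sample. There are two drawbacks. Attribution is harder once conventional red cells may be given after Day 7. Subjects who have already completed Day 75 would not be captured prospectively; enrollment began in November 2018 and this version post-dates the October 2021 re-estimation, so ascertainment would be uneven across the trial and the report should say so.
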